2.3 Safety parameters, adverse events and concurrent illnesses

The key safety parameters are the serious and significant adverse events listed in [REDACTED] (adverse events are classified as 'serious', 'significant' or 'non-significant'). Clinical assessment is made at the study visit(s) for these parameters. The presence of any ocular adverse event will be recorded on the eCRF and reported to the Sponsor using CVI report forms, and those ocular adverse events described as 'serious' or 'significant' will be detailed in the final report. Similarly, any concurrent illness that is likely to impact on the relevance and quality of the captured data will be noted on the case report form.

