1.1 Background

The transmission of COVID-19 is thought to occur mainly through small droplets released after coughing, sneezing and through contact with contaminated surfaces. Use of personal face masks (PFM) is considered to be one of the most important strategies for protecting the wearer from this and other infectious diseases.

Although PFM is aimed to protect the user, it has the potential to negatively impact upon day to day tasks as well as individual work performance. Face protection such as masks, goggles and face shields are often worn for hours at a time and anecdotal evidence suggests that use of prescribed spectacles in combination with PFM can be difficult. One of the most common problems encountered is fogging of spectacles whilst wearing a face mask. This can result in significantly impaired vision which may interfere with the performance of daily activities. Furthermore, the use of spectacles with masks and other forms of PFM is physically uncomfortable. One way to potentially overcome these issues is to fit contact lenses.

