2.6.3 Surgical masks

Subjects will be supplied with disposable surgical masks (Type I or Type II). Surgical masks should be worn for a minimum of one hour per day, four days per week. Subjects will be asked to wear the surgical mask for the majority of time that they need to wear PFM. Surgical masks should not be reused and should be discarded after use.

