12. Slit lamp biomicroscopy will be carried out for the signs outlined in Table 4 and in accordance with the current Eurolens Research Standard Operating Procedure 'Examination of the anterior segment using slit lamp biomicroscopy'. Grades will be scored to the nearest 0.1 unit in the best judgement of the investigator using Efron Grading Scales. Corneal staining will be graded for five regions (central, superior, temporal, inferior and nasal) as well as an 'overall' grade. The predominant type of corneal staining present will also be recorded.

Classification	Primary signs	Secondary signs
Signs	Conjunctival redness Limbal redness Corneal neovascularisation Epithelial microcysts Corneal oedema Corneal staining Location of staining Conjunctival staining Papillary conjunctivitis	Bephrats Meibomian gland dysfunction Mucin bands
Score	Efron Grading Scores (scored to nearest 0.1)	Efron Grading Scores (scored to nearest 0.1) (except mucin bands, where the number is recorded)

[figure not shown]
Table 4: Biomicroscopic signs. Staining assessed with sodium fluorescein.

The presence of any adverse events will be recorded [REDACTED]

13. The investigator will confirm that the subject satisfies all the inclusion and exclusion criteria. Subjects who fail to meet all the criteria at this time will usually be discontinued and replaced.

14. The subject will be randomised to one of the two treatment groups. For subjects assigned to the spectacle group, proceed to step 22.

15. For those assigned to the contact lens group, the study lenses will be fitted and allowed to settle for five minutes or until tearing stops (whichever is the longer).
16. Monocular logMAR visual acuity (high contrast) will be recorded before performing an over-refraction, and then monocular logMAR visual acuity (high and low contrast) will be carried out with the over-refraction in place, and in accordance with the current Eurolens Research Standard Operating Procedure 'The setup, measurement of visual acuity and procedures for carrying out an over refraction using Eurolens computerised logMAR VA chart'.

21. Subjects will be trained on contact lens application, removal and best practice immediately at the end of the visit or at a later date if required. More than one visit is possible for this 'teaching' session if there are problems with handling. Subjects will be dispensed with contact lenses only once the investigator is satisfied with their ability to successfully apply and remove lenses.

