3.2.3 Follow-up visit

*For the contact lens group, subjects should attend wearing the study lenses which should have been *in situ* for at least two hours. Subjects who attend without lenses *in situ* for at least two hours will usually be rescheduled. For the spectacle group, subjects should attend wearing their spectacles. Spectacles should have been worn for a minimum of two hours on the day of the visit.*

The following procedures will be performed:

1. Any medical or ocular issues since the last visit.
2. Spectacle or contact lens wearing times since the previous visit (hours per day, days per week and comfortable hours per day).
3. Spectacle or contact lens wearing time on study visit day.
4. Surgical mask wearing times since the previous visit (hours per day, days per week and comfortable hours per day).
5. [REDACTED]
6. Facemask usability questionnaire will be completed [REDACTED]
7. [REDACTED]
- [REDACTED]
- [REDACTED]
- [REDACTED]
- [REDACTED]

[REDACTED]

[REDACTED]

[REDACTED]

[REDACTED]

[REDACTED]

8. Questions about using the mask during day-to-day activities/tasks [REDACTED]

[REDACTED]

9. [REDACTED]

[REDACTED]

[REDACTED]

[REDACTED]

[REDACTED]

[REDACTED]

[REDACTED]

[REDACTED]

[REDACTED]

11. For spectacle wearers, monocular logMAR visual acuity (high contrast) will be recorded. Proceed to step 15.

12. For contact lens wearers, monocular logMAR visual acuity (high contrast) will be recorded before performing an over-refraction, and then monocular logMAR visual acuity (high and low contrast) will be carried out [REDACTED] as described in section 3.2.2.

13. [REDACTED]

[REDACTED]

[REDACTED]

[REDACTED]

15. The subject will be issued with their payment and discharged.

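### Section 2.3 commits the final report to detail only serious or significant ocular adverse events, leaving recorded minor ocular and non-ocular events without a stated place in it

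*Combined protocol and SAP*

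**What the plan says.** Section 2.3 of the combined protocol and SAP makes serious and significant adverse events the key safety parameters and adds a third, non-significant class. The list that defines the classes is redacted. Three rules follow in that section:

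- Recording: "The presence of any ocular adverse event will be recorded on the eCRF and reported to the Sponsor using CVI report forms". This covers all three classes, but only ocular events.
- Reporting: "those ocular adverse events described as 'serious' or 'significant' will be detailed in the final report".
- Other illness: "any concurrent illness that is likely to impact on the relevance and quality of the captured data will be noted" on the case report form. The test for entry is the effect on the data, not harm to the subject.

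Other sections reach further. In section 3.2.2, step 12, under the table of slit lamp signs, the plan says: "The presence of any adverse events will be recorded" (the rest of the sentence is redacted). In section 3.2.3, step 1 of the follow-up visit asks for "Any medical or ocular issues since the last visit", before the two arms take different steps. Section 2.3.2 requires notification of the sponsor's contact for any serious or significant event, ocular or not. Section 2.2 has all discontinuations recorded and lists discomfort among the possible reasons.

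**The concern.** The plan collects more about harm than it undertakes to report. Two kinds of event drop out between the eCRF and the commitment in section 2.3: ocular events in the lowest class, and non-ocular events of any class.

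Both kinds are relevant here. One arm consists of people new to contact lenses, so a minor ocular event is a natural thing to look for. Both arms are given a mask to use as part of the study ("Surgical masks should be worn for a minimum of one hour per day, four days per week"), so a non-ocular complaint could arise in either. A rule that leaves these out can hide events in either direction.

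What is at stake is how the harms section will be read. If it lists nothing, a reader may conclude that nothing happened, when the correct statement may be that nothing passed the reporting rule. The draft report also goes to the sponsor's contact for comment and possible re-drafting (section 4.1), which is a further reason to fix the content of the harms section beforehand.

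**Working it through.** **No figure to reproduce.** The visible text gives no adverse event rate and no safety calculation, and section 1.5.1 is redacted. All event risks below are assumptions, shown over a range.

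**Inputs from the plan.** Section 2.1: 15 completers intended per group, so n = 15 for the lens arm and n = 30 for both arms. Section 3.1: follow-up target 14 days, allowable range 10-20 days.

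**Step 1. The text, by type of event.**

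| Event | Where it is recorded | Commitment to detail it in the report |
|---|---|---|
| Serious or significant, ocular | eCRF and sponsor form (2.3) | Yes (2.3) |
| Non-significant, ocular | eCRF and sponsor form (2.3) | None stated |
| Serious or significant, non-ocular | Sponsor's contact notified (2.3.2); step 1 at follow-up | None stated |
| Non-significant, non-ocular | Step 1 at follow-up; case report form if data quality is affected (2.3) | None stated |

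The sentence in section 3.2.2 on recording any adverse events belongs to step 12 of the initial visit, and randomisation is step 14. In the visible text, the wider recording rule is therefore stated before treatment is assigned. Only step 1 of the follow-up visit carries the wider enquiry past randomisation.

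**Step 2. Chance that no event is detailed.** With risk p per subject of a serious or significant ocular event over the two weeks, P(none) = (1 − p)^n.

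| Assumed p | n = 15 (only the lens arm at risk) | n = 30 (both arms at the same risk) |
|---|---|---|
| 1% | 0.99^15 = 86% | 0.99^30 = 74% |
| 2% | 0.98^15 = 74% | 0.98^30 = 54.5% |
| 5% | 0.95^15 = 46% | 0.95^30 = 21.5% |
| 10% | 0.90^15 = 21% | 0.90^30 = 4% |

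An empty section is more likely than not only if p is below 1 − 0.5^(1/n). That is 4.5% for n = 15 and 2.3% for n = 30.

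**Step 3. What a zero would mean.** The one-sided 95% upper limit after zero events is 1 − 0.05^(1/n): 18.1% for n = 15 and 9.5% for n = 30.

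**Step 4. What the rule could leave out.** If 5-20% of lens wearers had a non-significant ocular event (assumption), 15 × 0.05 = 0.75 to 15 × 0.20 = 3 such subjects would be expected, and section 2.3 does not require any of them to be detailed.

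**Step 5. What a full table would show.** If the risk of any recorded event in an arm of 15 were 5%, 10% or 20% (assumption), the chance of at least one entry, 1 − (1 − p)^15, would be 54%, 79% or 96.5%. A comparison of arms would still be weak. For 10% against 30% with 15 per arm, two-sided 5%, normal approximation: standard errors √(2 × 0.2 × 0.8/15) = 0.146 under equality and √((0.09 + 0.21)/15) = 0.141 otherwise. Then (0.20 − 1.96 × 0.146)/0.141 ≈ −0.61, and power is about 27%.

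**The case against.** The strongest reply is that section 2.3 sets a minimum. It says what will be detailed, not that everything else will be left out. Section 2.1.1 includes all subject data in the final analyses unless there are strong grounds against, and section 3.4 has unused data detailed and discussed in the report. On that reading, minor events on the eCRF would reach the report anyway. This stands in part: nothing forbids reporting them. But the general clauses do not clearly override a specific rule on adverse events, and neither provides a summary of harms by arm.

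Two stronger readings are tempting, and the documents do not support them.

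- A reader might infer that only ocular events are recorded. Section 3.2.2 (step 12), section 3.2.3 (step 1) and section 2.3.2 are not limited to ocular events in their visible text. The gap is in what must be reported.
- A reader might infer that harm from wearing spectacles with a mask can never count. Section 1.1 does say of fogging that "This can result in significantly impaired vision which may interfere with the performance of daily activities". But mask comfort, including breathability, heat, tightness and ear-lobe comfort, is scored in both arms at both visits, and questions on daily tasks are asked at both visits. The principal hypothesis in section 1.5 compares subjective scores. These problems are handled as outcomes. All that can be said is that the visible text gives them no route to be reported as adverse events.

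The redacted class list also means that nobody can say from this text how a given mild event would be classed. That limits any example, but not the point: wherever the line is drawn, the lowest class is outside the reporting commitment.

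Finally, this is an exploratory two-week study of about 30 people with a CE-marked lens, so the consequence is modest. That is fair. It bears on the importance of the point, not on whether the gap exists.

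**Conclusion.** The point holds as a gap in reporting. Section 2.3 commits the report to a subset of the adverse events that the plan itself collects, and sections 2.3 and 3.2.2 differ on whether recording is limited to ocular events.

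Its size is conditional. A reader might infer that the harms section will probably be empty. That follows only if the two-week risk of a serious or significant ocular event is below about 4.5% per subject (only the lens arm at risk) or 2.3% (both arms at the same risk), and the documents give no rate. It would also concern detailed adverse events, not all signs of harm, because visual acuity, comfort scores and discontinuations are collected too. What does not depend on any assumed rate is that zero events in 15 would leave risks up to 18% open.

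A reader might also suspect unequal follow-up, since spectacle wearers go from step 11 to step 15 at the final visit. Much of the text between step 12 and step 15 is redacted, so this can be neither confirmed nor excluded.

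The change is worth making because it is cheap and removes a selective rule. It would not turn this study into a test of safety.

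**What to change.** 1. Reconcile sections 2.3 and 3.2.2, so that one rule states which adverse events are recorded and applies to both arms at every visit, including follow-up.
2. Replace the reporting clause in section 2.3 with wording such as: *The final report will tabulate, by randomised arm, all recorded adverse events, ocular and non-ocular, in all three classes, including medical issues recorded at step 1 of the follow-up visit. Narratives will be given for serious and significant events. Where a count is zero, the upper confidence limit will be shown. The table is descriptive; no test between arms is planned.*
3. Show events recorded before randomisation at the initial visit separately from later ones.

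The cost is one more table from information that the plan already collects, and minor events become visible in the report. No visit or treatment changes. The fix does not ask subjects to attribute events to the mask or to their vision correction, or to log mishaps from fogging. Neither is visibly collected at present, so adding them would be new data collection.

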2.3.1 Investigator obligations

At all times the investigator will act in the best interest of the subject. Referral or treatment of an adverse event or other clinical finding should be initiated in the best clinical judgement of the investigator, irrespective of the participation in the clinical study.

2.3.2 Reporting obligations

In the case of a 'serious' or 'significant' adverse event, the Principal Investigator will notify the Industrial Contact Person as soon as possible. Manchester UREC and any regulatory authorities will be informed as required.

2.4 Study termination

If it becomes necessary to terminate the study earlier than planned, the Industrial Contact Person will notify the Principal Investigator who will end the study with the cooperation of other staff members. Manchester UREC will be informed.

2.5 Protocol deviations

Any deviations from this protocol will be recorded, and reported to the Industrial Contact Person as appropriate. Manchester UREC will be informed as necessary.

2.5.1 Protocol amendments

Any amendments will be agreed between the Industrial Contact Person and the Principal Investigator with the cooperation of other staff members. Amendments will be recorded, identified and distributed. Approval from Manchester UREC will be obtained as necessary.

2.6 Study resources

Study products will be stored according to the manufacturer's product instructions.

2.6.1 Lenses

Details of the study lens are provided in Table 2. The lens is CE marked. Initial lens selection will be as indicated by the manufacturer fitting guidelines.

Name	car t 1 day
Manufacturer	CooperVision Inc
Mater a	somof con A
EWC (%)	56
BOZR (mm)	8.6
D ameter (mm)	14.1
Spherica powers (D)	+8.00D to -10.00D (0.50D steps after +6.00D and -6.00D)

Table 2: Study lenses.

2.6.1.1 Use of lenses

Study contact lenses will be worn on a daily wear, daily disposable basis (i.e. removed at end of day and discarded). Lenses should be worn for a minimum of eight hours per day, five days per week. The lenses are also to be worn for a minimum of two hours before attending the follow-up visit.

2.6.2 Care regimen

No care system will be used on this study.

2.6.3 Surgical masks

Subjects will be supplied with disposable surgical masks (Type I or Type II). Surgical masks should be worn for a minimum of one hour per day, four days per week. Subjects will be asked to wear the surgical mask for the majority of time that they need to wear PFM. Surgical masks should not be reused and should be discarded after use.

2.6.4 Inventory control

All study lenses will be supplied by CooperVision Inc. All worn and unworn lenses will be discarded. There will be an accurate accounting of the study test product at the completion of the study. All used study test products will be documented (Lot number; Expiry date etc.) in the study paperwork or CRF.

2.6.5 Clinical equipment

Clinical equipment is regularly maintained and calibrated as required. Standard operating procedures and international standards are used where appropriate.

2.7 Study control

Bias will be minimised by randomising the treatment allocation. Eligible subjects will be randomly assigned to one of two treatment groups (contact lens or spectacles) using computer-generated random numbers.

2.8 Documentation

Documents related to this work that require archiving will be kept by Eurolens Research for a period of 20 years after completion of the final report. The Sponsor company's permission will be sought before the documents are destroyed.

2.9 Data collection and analysis

Data collected in this work will be recorded on a custom-developed database and an established data trail. Data handling will include export of the study information from the clinical database into spreadsheet format for manipulation, followed by export into a statistical package for analysis. Most clinical data will be entered directly onto the electronic case report form and are considered to be source data.

2.10 Study completion

The clinical phase of the study will be considered as complete when all subjects have attended their last visit.

2.11 Confidentiality

All matters related to this work will remain confidential within Eurolens Research, the funding company and any regulatory authority (e.g. Manchester UREC). Eurolens Research will take all reasonable steps to ensure that specific lens-related information is not passed on to study participants unless this is required for clinical management of an adverse event. Personal subject information will not be made available without explicit consent. Subjects will only be referred by their unique identity number in the study report. The data activities of Eurolens Research are registered with the data protection officer at The University of Manchester.

2.12 Study monitoring

In order to provide quality control and quality assurance as part of this work, the study monitor will:

1. Liaise closely with the Principal Investigator.
2. Monitor and ensure the safety of the subjects.
3. Ensure that the investigation is being conducted according to the protocol.
4. Monitor and review (or oversee review of) the study records to ensure accuracy.

5. Document their observations and make them available to relevant authorised parties (e.g. Manchester UREC).
6. Implement the Eurolens Research clinical monitoring standard operating procedure.

2.13 Clinical trial registration

This study will be registered with clinicaltrials.gov in accordance with section 801 of the Food and Drug Administration (FDA) Act which mandates the registration of certain clinical trials of drugs and medical devices.

Section 3. Subject management

3.1 Visit scheduling

Subjects will be required to attend two visits – an initial visit and one follow-up visit. Acceptable date ranges are shown in Table 3. Subjects in the contact lens group may need to attend for more than one ‘teach’ session.

Vst	Target	Allowable range
Initial vst	N/A	N/A
2 week Follow-up	14 days from dispensing 1	10-20 days from initial vst

Table 3: Visits and allowable ranges.

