2.1.1 Subject withdrawal and replacement

This study includes two clinical visits. Once the study consent form is signed, the subject is considered to be enrolled on the study. Subjects who have signed the consent form, but who have not completed the dispensing visit will usually be replaced. All subject data will be included in the final analyses unless there are strong grounds for exclusion; such grounds will be detailed in the final report.

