22. For both groups: Subjects will be supplied with disposable surgical masks (Type I or II) and will be asked to wear them for the majority of time that they need to wear PFM (for at least one hour per day for at least four days per week). Subjects will receive instructions on how to wear the surgical mask.

Subjects will then be discharged and asked to return for the two-week follow-up visit.

- a. Subjects in the contact lens group will be asked to attend the follow-up visit after having worn the study lenses for at least two hours. They should be asked to wear their lenses for a minimum of eight hours per day, five days per week. No formal 'building up' of wearing time will take place, instead subjects will be asked to wear their contact lenses for as long as they are comfortable until they have achieved the required 8 hour minimum wear time. Some subjects may achieve this on the first day of wear, others may take a few days before they are happy to wear for 8 hours, but all subjects should progress to a minimum of 8 hours per day as soon as they are able.
- b. Subjects in the spectacle group will be asked to wear their spectacles for a minimum of 8 hours per day, 5 days per week. They should attend the follow-up visit having worn spectacles for a minimum of 2 hours on the day of the visit.
- c. Subjects should use PFM for at least one hour per day for at least four days per week.

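### Table 3 counts the follow-up target from dispensing but the allowable range from the initial visit, so late lens dispensing shortens the permitted exposure in the lens arm only (minor)

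*Combined protocol and SAP*

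**What the plan says.** The protocol plans two visits, with a two-week wearing period between them. Table 3 in section 3.1 gives the follow-up target as "14 days from dispensing 1" and the allowable range as "10-20 days from initial vst". The numeral after the word dispensing is not explained in the visible text.

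The paragraph above the table adds: "Subjects in the contact lens group may need to attend for more than one" teaching session. Section 3.2.2, step 21, places lens training "immediately at the end of the visit or at a later date if required", and then sets a condition: "Subjects will be dispensed with contact lenses only once the investigator is satisfied with their ability to successfully apply and remove lenses". The spectacle arm skips these steps and goes from randomisation (step 14) to step 22, which begins "For both groups: Subjects will be supplied with disposable surgical masks".

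Section 2.1.1 mentions a dispensing visit when it says that consented subjects "who have not completed the dispensing visit will usually be replaced". It gives no time limit. No visible text moves the allowable range when dispensing is late.

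**The concern.** The two cells share an anchor only when lenses are dispensed on the day of the initial visit. The protocol itself provides for later dispensing, and all subjects are new to contact lenses (section 2.1.3, criterion 4), so some handling problems are foreseeable. Each day of delay then takes a day off the shortest and the longest permitted lens exposure, while the spectacle arm is untouched.

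The follow-up visit is the only scheduled visit that collects outcomes of the wearing period. A lens-arm visit well short of two weeks could count as in window and so not be recorded as a deviation under section 2.5. Step 22a notes that some lens wearers reach the required daily wear at once but "others may take a few days before they are happy to wear for 8 hours". A short interval could therefore contain a larger share of adaptation in one arm than the plan intends.

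**Working it through.** **Inputs.** Target of 14 days, printed as counted from dispensing; range of 10 to 20 days, counted from the initial visit (both Table 3). Later dispensing is possible in the lens arm only (section 3.2.2, steps 14 and 21). Let d be the number of days from initial visit to dispensing. The documents give no value for d, so every value above 0 is an assumption.

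**Formulas.**
- Permitted days since dispensing, lens arm: 10 − d to 20 − d.
- Target day counted from the initial visit, as printed: 14 + d. It lies in the range if 14 + d ≤ 20, that is, if d ≤ 6.
- The range contains 20 − 10 + 1 = 11 days. For d from 0 to 10, d of these fall less than 10 days after dispensing.
- Spectacle arm: always 10 to 20 days.

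**Plan's own figures.** At d = 0 the range is 10 to 20 days after dispensing and the target is day 14. The two cells agree.

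| d (assumed) | Permitted days since dispensing, lens arm | Target day from initial visit | Target in range? | Allowed days under 10 since dispensing |
|---|---|---|---|---|
| 0 | 10 to 20 | 14 | yes | 0 of 11 |
| 1 | 9 to 19 | 15 | yes | 1 of 11 |
| 3 | 7 to 17 | 17 | yes | 3 of 11 |
| 6 | 4 to 14 | 20 | yes, on the last day | 6 of 11 |
| 7 | 3 to 13 | 21 | no | 7 of 11 |

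The window around the printed target runs from −(4 + d) to 6 − d days: −4/+6 at d = 0, −7/+3 at d = 3, −10/0 at d = 6. At d = 7 it closes one day before the target.

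**Three readings of the text.**
1. *As printed:* the table applies. Both cells can be met for d = 1 to 6 but not from d = 7.
2. *The target cell also refers to the initial visit* (its wording is damaged): the cells agree, but a visit exactly at target is 14 − d days after dispensing, that is 11, 8 and 7 days at d = 3, 6 and 7. The range still shortens lens exposure.
3. *The initial visit runs until dispensing:* d = 0 for everyone and nothing is inconsistent.

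**After a common anchor.** If both cells count from dispensing in the lens arm, the range is 10 to 20 days after dispensing for every d, and the target always lies inside it at −4/+6 days.

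**The case against.** The strongest reply is the third reading. Section 3.1 speaks of only two visits, training and discharge are numbered steps within the initial-visit section, and section 2.1.1 mentions a dispensing visit in a paragraph that also says there are two visits. On that view the initial visit ends at dispensing and both cells share one anchor. This is not excluded. Step 21 weighs against it, because it contrasts the end of the visit with a later date and calls further teaching another visit. The ambiguity stands and the sponsor needs to settle it.

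Second, staff book to the target. As printed, that is 14 days after dispensing and lies inside the range for every delay up to six days. A short exposure then needs both a delay and attendance before target. This stands, and it is a main reason why the point is minor.

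Third, the table is damaged in extraction, and the visible step numbers jump from 16 to 21. A reader might infer that the plan sets no limit on the delay. The documents support only that no limit is visible.

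Fourth, the follow-up visit records wearing times since the previous visit (section 3.2.3, steps 2 to 4), so some exposure data exist by arm. As described, these are hours per day and days per week, not elapsed days since dispensing.

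Finally, a reader might infer that short-interval visits would mostly measure adaptation. At d = 3 the earliest permitted visit is still 7 days after dispensing, and step 22a speaks of a few days at most for some subjects. That inference fits only a delay of about a week combined with a visit at the very start of the range, and no passage suggests such a delay is expected.

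**Conclusion.** As printed, the two cells of Table 3 do not share an anchor. Unless the initial visit is meant to run until dispensing, a delay of d days makes the permitted lens exposure 10 − d to 20 − d days against 10 to 20 in the spectacle arm, and from d = 7 the plan's own target falls outside its range. The arithmetic is certain; d is assumed throughout.

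Two stronger conclusions are tempting. One is that the comparison of arms will be biased against, or in favour of, contact lenses. The documents give neither the frequency nor the length of delays, so neither the size nor the direction of any bias can be stated. The other is that time with the supplied masks already differs between arms. Only the spectacle arm is told to skip ahead to step 22, so the natural order in the lens arm is dispensing first and masks second. Mask time longer than in the spectacle arm would arise only if masks were given out before dispensing and the range were then re-anchored on dispensing. That is a matter to confirm, not an error in the plan.

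With scheduling to target protecting delays of up to six days, this is a minor point that is cheap to put right.

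**What to change.** - Reconcile the two cells of Table 3 to one stated anchor. One example is the start of the allocated correction in the study: lens dispensing in the lens arm, the initial visit in the spectacle arm. This gives both arms the same permitted exposure and changes nothing when dispensing is on the same day. If the initial visit is already meant to end at dispensing, saying so in section 3.1 achieves the same.
- Confirm that mask supply (step 22) follows dispensing in the lens arm, as the order of the steps implies. If it did not, the example anchor would make lens-arm mask time 10 + d to 20 + d days.
- Report days since the start of the allocated correction by arm. This needs the dispensing date on record.

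**Cost.** A one-row amendment and a clarifying line, with ethics committee approval as necessary under section 2.5.1. Lens subjects whose dispensing is delayed may finish a few days later.
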